2.1 Study Hypotheses and Objectives

The study hypotheses are as follows:

- 1. That the intervention arm (daily contact testing) will have increased school attendance compared to the control arm (self-isolation) (i.e. superiority)
- 2. That the level of transmission of COVID-19 in the schools in the intervention arm (daily contact testing) is not inferior to (i.e. not higher than in) the control arm (self-isolation)

The primary objective of the study is to assess the effectiveness, in terms of in-school COVID-19 transmission and student / staff in-school days lost to self-isolation, of two different COVID-19 control strategies implemented at a school level using regular active case finding with lateral flow antigen tests.

Both arms of the study will include weekly active case finding of students and biweekly active case finding of staff. The arms will differ in the management of contacts of positive cases:

- (i) Arm 1: routine self-isolation of all first-order contacts of positive tests
- (ii) Arm 2: daily LFD testing of asymptomatic first-order contacts of positive tests at the beginning of the school day with self-isolation restricted to individuals with positive results.

Co-Primary End-Points

- (i) Number of school days lost from COVID-19 or contact with COVID-19 cases
- (ii) Estimated number and rate of within-school COVID-19 transmission events

Secondary End-Points

- (iii) Number and rate of positive contacts missed by daily LFD testing
- (iv) Number and rate of COVID-19 cases transmitted to the school-based and household firstorder contacts of the index case ("primary attack rate")
- (v) Number and rate of COVID-19 cases transmitted to the school-based and household second-order contacts of the index case ("secondary attack rate")
- (vi) Number and proportion of school attendees testing COVID-19 positive in weekly active case finding
- (vii) Proportion of student and staff first-order contacts who accept an offer of daily contact testing with LFD devices

Secondary objectives:

- 1. To gain knowledge on the operational aspects of this process; specifically, to understand uptake and barriers for schools and individuals as well as operational challenges.
- 2. To improve understanding of a range of behavioural factors, including reasons for participating, response to negative and positive test results, and compliance with self-isolation

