3.6 Assessment of End-Points

Please see the glossary at the start of this protocol for definitions

Co-Primary End-Points

(i) Number of school days missed among those eligible to be in school.

Daily school attendances will be obtained from the school register and absences recorded with reconciliation with COVID-19 associated absences. This will be compared between study arms, to historic schools' data, and to national schools' benchmark data collected via a survey of non-participating schools.

(ii) Estimated number of in-school COVID-19 transmission events

The number of positive cases will be obtained from the following sources:

- 1. Weekly LFD active case finding (Control and Intervention Arms)
- 2. Symptomatic individuals' NHS Test and Trace results obtained from Community Testing routine data (Control and Intervention Arms)
- 3. In-school LFD DCT testing (Interventional Arm).

Positivity rates will be reported for each source separately to facilitate like-for-like comparison between arms

Epidemiological links between cases will be obtained from the NHS Test & Trace Contact Tracing and Advice Service data base. Additional links will be obtained by membership of school-reported contact groups. Onward transmission from the index case will be determined by the following:

• Genomic sequence of virus: The additional PCR swab collected from positive individuals will be used to determine the whole genomic sequence of isolates. A sample of apparent links will be assessed with comparisons of whole genome sequencing. The diversity of genetic sequences both in the schools and the

community (routinely determined by COG) will be used to help interpret the results. Preliminary work currently undertaken will determine the appropriate genetic distance to be used to exclude a direct transmission event between individuals. This is likely to be 2 SNPs.

- Plausible epidemiological link (e.g. membership of same close contact group)
- For positive individuals identified in DCT the DMIC will review all available data to determine if the individual's infection was likely to have resulted from onward transmission from the index case, or via co-infection from an unknown 'upstream' positive or out-of-school positive case.

Secondary End-Points

(iii) Number of positive first-order contacts missed by daily LFD testing (Intervention arm only).

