3.9 Sample Size

Advice on the appropriate sample size for this study has been sought from [name] at the University of Oxford.

The challenge with setting a non-inferiority margin for transmission events is that the meaning of a non-inferiority margin is highly dependent on the control group event rate. For example, if the control group event rate is 20%, then, depending on the other advantages of the intervention, it may be reasonable to set a non-inferiority margin of 10%, i.e., to exclude increases of more than 10% absolute or 50% relative. But if the control group event rate is 1%, a 10% non-inferiority margin is very unlikely to be considered reasonable. However, choosing the wrong control rate can have enormous consequences for the power of a trial to determine non-inferiority within a pre-defined bound⁸.

At present, it is extremely difficult to get any estimate of a control group event rate for transmission over the next 3 months, and hence it is impossible to pre-define what might be a meaningful non-inferiority margin, given the hypothesised benefits of the intervention. We therefore power the trial to determine superiority of the intervention on school attendance; if superiority is demonstrated on the primary endpoint, we will ask an independent committee to judge whether the 95% CI for the difference between intervention and control schools on transmission events is sufficiently close to no difference such that the benefits outweigh any potential risks.

The primary endpoint of the study is the number of missed days at school compared to the control group. The following scenarios will illustrate the effect of the intervention on school attendance

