5.3 Results Data Monitoring

During the trial the combined results of all schools in the trial will remain blinded to all except the statistical centre and the Independent Data Monitoring Committee (IDMC). The IDMC will review the overall quality, safety and efficacy of the data and make recommendations to the Trial Steering Committee on whether the trial protocol should be altered. If they have evidence beyond reasonable doubt that one strategy is clearly superior (or inferior) to another arm and that the result is likely to change public health practice, they should immediately report the unblinded data and their recommendation to the Trial Steering Committee.

Statistical Analysis of primary and secondary end-points

Conventional statistical analysis will be undertaken. Analysis will be undertaken for the primary objective at a per-school basis with comparisons to the population of control schools. Absent school days (both total and COVID-related) will be presented as a proportion of pupils (with binomial confidence intervals). Unadjusted transmission events will be measured as the incidence of all COVID-19 positive cases determined by both Pillar 2 and school directed testing. Transmission events will also be categorised as 'more likely' if they either have a similar genetic sequence (the cut off to be determined) or as a member of the same predefined school bubble.

Secondary analysis

The performance of DCT will be made at the level of each primary contact. The performance of the DCT will be compared to PCR using conventional exact binomial statistics. The extent of secondary transmission events will be analysed using Poisson statistics and the results

stratified according to the LFD and PCR results of the DCT-contact. The results can also be adjusted according to the day that the LFD becomes positive and the CT value of the PCR result.

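### Co-primary (ii) is within-school transmission, but section 5.3 measures all positive cases, sections 3.6 and 5.3 classify linked cases differently, and section 3.9 does not say which measure's 95% CI is judged

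*Protocol*

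**What the plan says.** Protocol 2.1 lists co-primary (ii) as "Estimated number and rate of within-school COVID-19 transmission events". Hypothesis 2 is that transmission in the schools of the daily contact testing (DCT) arm is no higher than in the self-isolation arm.

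Protocol 3.6 draws positive cases from three sources: weekly lateral flow testing and symptomatic NHS testing in both arms, and DCT in the intervention arm only. On these it says "Positivity rates will be reported for each source separately to facilitate like-for-like comparison between arms". It continues: "Onward transmission from the index case will be determined by the following", and gives three elements: sequencing of a sample of apparent links, with a genetic distance (probably 2 SNPs) beyond which direct transmission is excluded; a plausible epidemiological link; and individual review of positives found in DCT.

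Protocol 5.3 gives a different account. "Unadjusted transmission events will be measured as the incidence of all COVID-19 positive cases determined by both Pillar 2 and school directed testing". Then: "Transmission events will also be categorised as 'more likely' if they either have a similar genetic sequence", with the cut-off left open, or if the cases belong to the same predefined bubble.

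Protocol 3.9 sets no non-inferiority margin. If attendance shows superiority, an independent committee is to "judge whether the 95% CI for the difference between intervention and control schools on transmission events is sufficiently close to no difference". It does not say which transmission measure the interval is for.

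**The concern.** The endpoint, its measurement and the decision refer to three different things. The endpoint is spread within schools. The first measure in 5.3 is total infection among attendees, wherever acquired. The decision in 3.9 concerns transmission events with no definition attached.

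With no margin, the committee's reading of the interval is the whole inferential step for hypothesis 2. If the measure behind that interval is not fixed, the same data can yield intervals that point to different conclusions, and nothing in the protocol says which governs. This goes beyond missing detail: a statistical analysis plan that followed 5.3 would depart from 2.1 and 3.6, and the reverse.

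**Working it through.** **1. The passages side by side**

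- Endpoint (2.1): events within school.
- Lead measure in 5.3: all positives, pooled over symptomatic and school testing, wherever acquired.
- A same-bubble pair with discordant sequences: more likely transmission under 5.3 (sequence *or* bubble); excluded as direct transmission under 3.6.
- Individual review (3.6): written for positives found in DCT, which exist in one arm only.
- Decision (3.9): a 95% CI, measure not named.

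**2. Planning rates**

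The protocol states no sample size, power or margin for transmission, so there is no figure of its own to reproduce there. Its attendance figures serve only to confirm the planning rates. Section 3.9 gives 1 index case per school per month in control. For intervention, the prose says 2 per week and Table 1 says 2 per month. The stated 360 missed days per month fits 2 per month: 2 × (15 + 1 + 2) × 10 = 360. So does Table 2. For 15 self-isolating at 60% consent over two months, the index cases are m1 = 2 and m2 = 4, and the isolators per index case are a = 51 and b = 15 + 3 = 18:

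n = (1.960 + 0.842)² × (m1a² + m2b²) / (m1a − m2b)² = 7.849 × 6,498 / 900 = 56.7, so 57 against the tabulated 58.

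I therefore use 2 per month.

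**3. Detection alone, on the protocol's planning figures**

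With 50 schools and 2 months per arm (100 school-months), control has 100 index cases and intervention has 200. Two DCT positives per index case add 400. Rate ratios (RR) have log-scale Poisson 95% CIs, standard error √(1/x₁ + 1/x₀). Clustering is ignored, so real intervals would be wider.

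| Measure | 60% consent in intervention | 40% consent |
|---|---|---|
| All positives, DCT included | 600 v 100: RR 6.00 (4.86 to 7.41) | 4.00 (3.21 to 4.98) |
| All positives, DCT excluded | 200 v 100: RR 2.00 (1.57 to 2.54) | 1.33 (1.03 to 1.73) |
| Per weekly-testing consenter | RR 1.00 (0.79 to 1.27) | 1.00 (0.77 to 1.30) |

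The last row equals 1 by construction, because planned detection is proportional to consent. The first row is an upper illustration: the planning figures give no count for control contacts who later test positive.

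**4. Dilution, if detection were equal**

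Let f be the share of control cases acquired in school (not in the protocol; assumed) and R the true within-school ratio, with other infections equal between arms. The all-case ratio is 1 + f(R − 1). For R = 1.5 it is 1 + 0.2 × 0.5 = 1.10 at f = 20%, and 1 + 0.5 × 0.5 = 1.25 at f = 50%.

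Intervals with an assumed 100 control positives per 100 school-months:

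| f, R | All cases | Within-school |
|---|---|---|
| 20%, 1.5 | 1.10 (0.84 to 1.44) | 1.50 (0.85 to 2.64) |
| 20%, 2 | 1.20 (0.92 to 1.56) | 2.00 (1.17 to 3.42) |
| 50%, 2 | 1.50 (1.16 to 1.93) | 2.00 (1.42 to 2.81) |

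Dilution acts on the ratio. On the rate difference, unrelated cases leave the estimate unchanged and add noise: at f = 20%, R = 2, both measures give +0.20 per school-month, with −0.09 to 0.49 for all cases and 0.05 to 0.35 for within-school events. The intervals still disagree about zero.

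**5. Size of the classification conflict**

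If 10% to 70% of the 400 DCT positives were genetically discordant with their index case (assumed) and all were sequenced, 5.3 would count 400 and 3.6 would count 360 to 120.

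**The case against.** The strongest reply is that 2.1 names the endpoint and the choice of operational version belongs in the analysis plan. Section 5.3 can be read as an unadjusted measure followed by a refinement, since its second sentence is introduced as an addition. That reading is fair, but it makes total infection the lead measure of a within-school endpoint, and it leaves the clash with the genetic exclusion rule in 3.6. Source-specific positivity is a reporting breakdown rather than a rival endpoint; that part of the reply stands.

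Three stronger readings are tempting and the protocol does not support them.

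- *The linked measures are free of dilution.* They are not. Bubble membership alone suffices in 5.3, section 1 says a group of contacts can be a whole year group of over 250 pupils, and 3.6 sequences only a sample of links. Coincident community infections enter both.
- *All-case incidence is biased toward no difference and so favours DCT.* That holds for the ratio only under equal detection. The protocol expects higher uptake and additional DCT positives in the intervention arm, which push pooled incidence against DCT.
- *The choice of measure inflates a false-claim rate or yields opposite verdicts.* There is no margin and no rule allowing a claim on any one of several measures. A committee weighs an interval. What can be shown is conflicting intervals, and even these are not inevitable: in step 4 the two measures conflict in one of three scenarios.

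**Conclusion.** The point holds as a contradiction within the protocol. All-case incidence does not estimate the within-school endpoint of 2.1, sections 3.6 and 5.3 classify the same pair of cases differently, and 3.9 attaches the transmission judgement to an unnamed measure.

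The size depends on detection and on the in-school share. On the protocol's planning figures the ratio ranges from 1.00 per consenter to 2.00 or 6.00 pooled, with no difference in transmission assumed. With equal detection, a within-school ratio of 1.5 shrinks to between 1.10 and 1.25 for assumed shares of 20% to 50%. The error can therefore run in either direction. The shares, the count of 100 control positives in step 4 and the discordance range are assumptions. The textual conflict does not depend on them.

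**What to change.** Reconcile 2.1, 3.6, 3.9 and 5.3 as follows.

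- Name one measure as co-primary (ii) and as the basis of the committee's 95% CI: the per-school rate of within-school linked events.
- Define a linked event by one rule: an epidemiological link that is not excluded by sequence where a sequence is available. Remove the either/or wording in 5.3 or make it agree, and fix the genetic cut-off before the comparative data are seen.
- Apply the rule identically in both arms. The individual review in 3.6 cannot be used unchanged, because it covers DCT positives only.
- Count cases from sources common to both arms, and report DCT-only positives separately.
- Label all-case incidence as supportive and as estimating total infection in attendees. Label source-specific positivity as descriptive.

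All the data are already planned, so the cost is wording plus a classification procedure that also covers control cases. On the ratio scale the interval will be wider than for all-case incidence. Some misclassification remains where links are not sequenced. Restricting to common sources does not remove the effect of unequal weekly-testing uptake (step 3, second row), so the source-specific rates should be shown beside the named measure.

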A pragmatic cluster randomised trial in English secondary schools comparing the impact of a policy of weekly testing for COVID-19 followed by isolation of cases and their contacts, with a policy of weekly testing followed by isolation of cases and daily testing of contacts.

Study Sponsor: Department of Health and Social Care
Principal Investigator: [name]
Co-Investigators: [name], [name], [name], [name], [name]
Chief Data Analyst: [name]
Analyst: [name]

Affiliations

[name]	University of Oxford
[name]	Queen Mary University of London (NHS Test &
	Trace Public Health Lead)
[name]	University of Bristol
[name]	Department for Education
[name]	Department for Education
[name]	Public Health England
[name]	Department of Health and Social Care
[name]	Department of Health and Social Care

Document Approval

Role	Name	Signature	Date
Principle Investigator	[name]	[name]	22/02/2021
Chief Data Analyst	[name]	[name]	23/02/2021

A Note on Definitions

Throughout this protocol the following definitions are used. These are illustrated graphically in Figure 1 below

Index Case	The first known positive COVID-19 case in chain of transmission.
	This individual could be identified asymptomatically via LFD-based active case finding in the school or outside it, or via symptomatic NHS Test and Trace PCR testing
Bubble	Grouping within school created by school to limit transmission of SARS-CoV-2 within the schools. Bubbles are meant to be distinct entities with no intermixing (i.e. a member of Bubble A should have no contact with members of Bubbles B, C, D, etc.)
First-Order Contact	Close contacts of the index case.
	The subset of a bubble identified by the school as being a close contact of an index case, as defined by Government guidance:
	https://www.gov.uk/government/publications/guidance-for- contacts-of-people-with-possible-or-confirmed-coronavirus-covid- 19-infection-who-do-not-live-with-the-person/guidance-for- contacts-of-people-with-possible-or-confirmed-coronavirus-covid- 19-infection-who-do-not-live-with-the-person
	These individuals will be eligible for Daily Contact Testing or self- isolation according to national guidelines (depending on study arm and consent status)
Second-Order Contact	Close contacts of a first-order contact.
	These individuals will be identified and assessed for COVID-19 status in order to measure the secondary attack rate in each arm of the study

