The number of Covid-19-associated missed days at school is dependent on the number of positive cases identified and the number of contacts of these cases that are self-isolating. Each positive case is self-isolated for 10 days. In the control group all first order contacts will also be self-isolated for 10 days. It is expected that this trial will occur in the summer term when the number of cases in a school will be low. For instance, it is expected that in the control group about 30% of children (and their parents) will consent to participate in regular weekly active case finding testing. For the purposes of the power calculation, it is assumed that the expected number of index cases identified is about 1 outbreak/month. Each index cases will lead to identification of 50 children in their bubble who will need to self-isolate each for 10 days. The number of index cases identified is a Poisson distribution with mean 1/month with each index cases leading to 510 missed school days.

In the intervention group, it is expected that a more complex set of interactions will occur. The ability to avoid self-isolation by DCT is likely to make participation in weekly active case finding testing more

⁸ Quartagrio et al, 'Handling an uncertain control group event risk in non-inferiority trials: non-inferiority frontiers and the power-stabilising transformation' (2020)

attractive with an increase in consent to voluntary weekly active case finding testing to 60%. This in turn will lead to the identification of more positive cases with initially an expected number of 2 different index cases identified per week. However, it is expected that 70% of children will volunteer for DCT and therefore only 15 children (25% of 50) will self-isolate. In addition, about 2 contacts will be identified by LFD testing as positive during DCT (5% of 35). It is expected that these 2 children will only have contacts within the bubble and therefore they will not lead to identification of more children. In all, each index cases will lead to the index cases or 360 missed schools / month

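### Section 5.3 counts every positive case, index cases included, as a transmission event, contrary to co-primary end-point (ii) and Section 3.6; the resulting bias can go either way

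*Protocol*

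**What the plan says.** Section 2.1 gives co-primary end-point (ii) as "Estimated number and rate of within-school COVID-19 transmission events". The definitions at the front of the protocol describe an index case as "The first known positive COVID-19 case in chain of transmission". Section 3.6 then sets the assessment: "Onward transmission from the index case will be determined by the following", after which it lists sequencing, a plausible epidemiological link, and, for positives found during DCT, a case review that considers co-infection and infection outside school.

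The statistical paragraph of Section 5.3 measures something else: "Unadjusted transmission events will be measured as the incidence of all COVID-19 positive cases determined by both Pillar 2 and school directed testing". It adds a second class: "Transmission events will also be categorised as 'more likely' if they either have a similar genetic sequence", or if they belong to the same bubble. It does not mention removing index cases from either count and does not say which count is the co-primary analysis.

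Section 3.9 sets no margin, because "it is impossible to pre-define what might be a meaningful non-inferiority margin". An independent committee is to judge the "95% CI for the difference between intervention and control schools on transmission events".

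**The concern.** An index case is where the known chain starts, so it is not known in-school transmission. Under Section 5.3 it is still an event. A pupil infected at home who has no positive contact scores 1 event; Section 3.6 gives 0. The outbreak in the footnote to Table 1, an index case plus 2 contacts positive on DCT, scores 3; Section 3.6 gives at most 2.

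This matters because end-point (ii) is the safety side of the trial. With no margin fixed, the committee has only the estimate, its interval and the event rate that gives them meaning. Section 3.9 itself says that what counts as an acceptable margin depends heavily on the control event rate. A count that mixes index and imported cases with in-school spread alters all three. The protocol also expects DCT to change how many index cases are found, so the added cases need not be equal in the two arms.

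**Working it through.** **Inputs from the protocol.** Control index cases: "The number of index cases identified is a Poisson distribution with mean 1/month with each index cases leading to 510 missed school days" (Section 3.9). Case-finding uptake is 30% in control and 40-60% under DCT, and Table 1 has 1 v 2 outbreaks per school per month. Fifty schools per arm are expected to sustain the trial, and Table 2 is for a two-month study. The protocol gives no number of onward cases, so that number is assumed below.

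**Check on the index rates.** The protocol has no power figure for transmission, but Table 2 shows which index rates it uses. Over two months, take the control mean as 2×51 and variance as 2×51². For DCT take mean L(m+3) and variance L(m+3)², with L = 2×uptake/0.30 and m the number isolating instead of testing. At m = 15 and 60% uptake, L = 4. The means are 102 and 72, and the variances 5202 and 1296. Then n = (1.96+0.842)²×6498/30² ≈ 57 by the normal approximation, and 58 with the noncentral t, as printed. At m = 18 the t calculation gives the printed 170. All 49 cells agree within tolerance. So Table 2 rests on index detection proportional to uptake: 1.33, 1.67 and 2 per month at 40%, 50% and 60%, against 1 in control. The text of Section 3.9 says 2 per week at one point, but Table 1, Table 2 and the 360 missed days (2×18×10) fit 2 per month.

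**Formulas.** Let I be index cases and T true in-school transmission events per school per month, with 0 for control and 1 for DCT.

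- All-case ratio = (I1+T1)/(I0+T0). This is a weighted average of T1/T0 and I1/I0, so it is pulled toward I1/I0.
- All-case difference = (T1−T0) + (I1−I0). The bias is I1−I0.
- Overstatement of the control rate = (I0+T0)/T0.

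**Results (control v DCT, per school per month).**

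| Index cases | True events | True ratio | All-case ratio | True difference | All-case difference |
|---|---|---|---|---|---|
| 1 v 1 | 1 v 1.5 | 1.50 | 2.5/2 = 1.25 | +0.5 | +0.5 |
| 1 v 1 | 2 v 3 | 1.50 | 4/3 = 1.33 | +1.0 | +1.0 |
| 1 v 2 | 1 v 1 | 1.00 | 3/2 = 1.50 | 0 | +1.0 |
| 1 v 2 | 1 v 1.5 | 1.50 | 3.5/2 = 1.75 | +0.5 | +1.5 |
| 1 v 2 | 1 v 3 | 3.00 | 5/2 = 2.50 | +2.0 | +3.0 |

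In the last row, transmission rises with the number of index cases detected (1 v 1.5 onward cases each). At 40% and 50% uptake the shift in the difference is 1.33−1 = +0.33 and 1.67−1 = +0.67.

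**Control rate.** With one index case per month and T0 = 0.5, 1 or 2, it is overstated 3.0-, 2.0- or 1.5-fold.

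**Precision with equal index rates.** Take 50 schools, two months, 1 v 1.5 true events and simple Poisson variance. Without index cases the totals are 100 v 150: difference 1.0 per school over two months, 95% CI 1.0 ± 1.96√250/50 = 0.38 to 1.62. With index cases they are 200 v 250: again 1.0, CI 1.0 ± 1.96√450/50 = 0.17 to 1.83.

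**The case against.** The strongest reply is that Section 5.3 calls this count unadjusted, follows it with the 'more likely' class, and can lean on Section 3.6 for linkage, review and positivity by source. Detailed counting rules may also sit in an analysis plan that is not shown. That is fair as far as it goes. But the protocol does fix this measure and does name it transmission events, and nothing in Section 5.3 ties the co-primary analysis to the Section 3.6 determination.

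A reader might infer that counting index cases always shrinks a true excess under DCT toward no difference. The documents do not support that. It requires a ratio, together with equal index rates or a true ratio above the index-case ratio. Section 3.9 names a difference, from which equal index counts cancel, and the wider interval makes reassurance about DCT harder, not easier. The protocol also expects unequal detection, which moves the difference against DCT.

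A reader might also infer that the 'more likely' class certainly counts the index case. The text is silent: a similar sequence can be read as a property of a link between two people.

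Finally, simply taking one case off every cluster would be too blunt. The index case is only the first known case and may have been infected in school, and linked cases may be co-infections. Section 3.6 recognises unknown upstream sources.

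**Conclusion.** The conflict is real: Section 5.3 labels all-case incidence as transmission events, against end-point (ii), the index-case definition and Section 3.6. Neither the unadjusted label nor the second category resolves it.

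No single direction of bias can be claimed. With equal index rates, the ratio is pulled toward 1, the difference is unbiased but less precise, and the inflated control rate makes a given excess look relatively smaller: 0.5 on 1.0 is presented as 0.5 on 2.0. With the protocol's expected detection, the difference gains between +0.33 and +1.0 per school per month against DCT. With no true excess and an assumed one event per school per month, the ratio then reads 1.50.

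The shift in the difference follows from the protocol's own index rates. The ratios, the overstatement and the intervals rest on assumed onward-case rates, and the intervals also on Poisson variance with no extra between-school variation. Infections acquired outside school that are not index cases add to the mixture and are not quantified here.

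**What to change.** In Section 5.3:

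1. Define the co-primary transmission count as cases judged under Section 3.6 to be onward in-school transmission. Do not count the index case of a chain unless that review links it to an earlier in-school case.
2. Apply the same exclusion to the 'more likely' count.
3. Report all positive cases under their own name, incidence of COVID-19 cases, by source as Section 3.6 already requires.
4. State that the determination is made on the same terms in both arms, since the case review in Section 3.6 is written only for positives found in DCT.

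The change is to wording. Schools already identify index cases for contact management, and the links and sequences are already to be collected. The price is fewer counted events and dependence on the completeness of the linkage data.
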